6.3. Adjustments for Covariates

The study is stratified by prediabetes status at randomization, country, and sex (female, male). Where necessary to be included as a stratification factor, countries with fewer than 10 randomized participants will be pooled into 1 category (pooled country).

Unless otherwise specified, for efficacy related analyses at 72 weeks, country/pooled country, sex, prediabetes status at randomization and corresponding baseline value will be used as a covariate. For efficacy analyses at 176 weeks (or 193 weeks), country/pooled country, sex and corresponding baseline value will be used as a covariate.

6.4. Handling of Dropouts or Missing Data

For the primary and key secondary efficacy endpoint analyses subject to type 1 error rate control, data for participants with missing values at the 72-week visit (or weight related measurements at

176-week visit for participants with prediabetes at randomization) will be imputed based on the method described in Section 6.13.1.3. However, for the parameters with only 1 postbaseline measure during the analysis period per schedule of activity, the last observation carried forward (LOCF) approach will be applied to impute the endpoint when ED measure is available.

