6.13. Efficacy Analyses

For submission of Study GPHK to the US FDA to support the registration of tirzepatide for chronic weight management, all primary and key secondary efficacy assessments will be guided by the “hybrid” estimand conducted using the FAS. Assessment of the primary and key secondary objectives (except for endpoint “delaying the onset of diabetes during 176 weeks or 193 weeks [for participants with prediabetes at randomization]”) will be conducted with multiple imputation of missing data (see Section 6.13.1.3).

For other regulatory agencies, publications and other purposes, the assessment of efficacy objectives will be guided by the “efficacy” estimand using the EAS.

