6.13.1.3. Methods for Imputations

For efficacy analyses relative to “hybrid” estimand, the intercurrent events (ICEs) and the resulting missing values will be handled as follows:

- Category 1: for missing data solely due to exceptional circumstances, such as pandemic or natural disasters (after other reasons for missing data are ruled out), the analysis will consider the missing data as missing at random. The missing data will be imputed using all non-missing data of the primary outcome measurement from the same treatment arm.
- Category 2: for missing data due to all other ICEs: missing data will be imputed based on retrieved dropouts in the same treatment arm, defined as observed primary outcome measurements, from participants in the same treatment group, who had their efficacy assessed after early discontinuation of the study drug. In case where there are not enough retrieved dropouts to provide a reliable imputation model (for example, the model implemented by the SAS program does not converge), an alternative multiple imputation method with reference to the placebo group (that is, placebo multiple imputation) will be used.

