6.13.2. Secondary Efficacy Analyses Subject to Type 1 Error Rate Control

Table GPHK.6.4. Secondary Measures Controlled for Type 1 Error

Objectives	Relative to the efficacy measure:	Analysis conducted in a manner similar to	Additional Information
Tirzepatide 10 mg and 15 mg combined is superior to placebo:	Mean change in body weight (kg) from randomization at 20 weeks	MMRM model in Section 6.13.1.1 for efficacy estimand and ANCOVA model in Section 6.13.1.2 for hybrid estimand	
Tirzepatide 5 mg is superior to placebo:	Mean percent change in body weight from randomization and percentage of participants achieving at least 5% body weight reduction at 72 weeks	Section 6.13.1.1 for efficacy estimand and Section 6.13.1.2 for hybrid estimand	
Tirzepatide 10 mg and/or 15 mg is superior to placebo:	Percentage of participants achieving body weight reduction $\geq 10\%$, $\geq 15\%$ and $\geq 20\%$ at 72 weeks	logistic model in Section 6.13.1.1 for efficacy estimand and logistic model in Section 6.13.1.2 for hybrid estimand	
	Mean change in waist circumference (cm) from randomization at 72 weeks	MMRM model in Section 6.13.1.1 for efficacy estimand and ANCOVA model in Section 6.13.1.2 for hybrid estimand	LSM estimates will be plotted by treatment through 72-weeks.

Secondary Measures Controlled for Type 1 Error

Objectives	Relative to the efficacy measure:	Analysis conducted in a manner similar to	Additional Information
Tirzepatide 10 mg and 15 mg combined is superior to placebo	Mean change in SF-36 v2 acute form Physical Functioning domain score from randomization at 72 weeks	ANCOVA model with the terms of treatment group, stratification factors as fixed effects, and baseline SF-36 v2 acute form Physical Functioning domain score as a covariate.	For efficacy estimand, missing data will be imputed based on LOCF method. For hybrid estimand, missing data will be imputed based on Section 6.13.1.3.
Tirzepatide (all doses combined) is superior to placebo:	Mean change in triglycerides, HDL-C, non-HDL-C, SBP and fasting insulin from randomization at 72 weeks	MMRM model in Section 6.13.1.1 for efficacy estimand and ANCOVA model in Section 6.13.1.2 for hybrid estimand	For hybrid estimand, missing data will be imputed first for each treatment based on Section 6.13.1.3, then combine all tirzepatide doses.

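### SAP 6.4's LOCF exception has no estimand limit, so for SF-36v2 Physical Functioning it conflicts with the hybrid imputation rule in Table GPHK.6.4 and SAP 6.13

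*SAP*

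**What the plan says.** Four places in the SAP bear on a missing Week 72 SF-36v2 Physical Functioning score.

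- **SAP 6.4, general rule.** In the type-1-error-controlled analyses, a missing Week 72 value is imputed by the method of Section 6.13.1.3.
- **SAP 6.4, exception.** The next sentence departs from that rule "for the parameters with only 1 postbaseline measure during the analysis period per schedule of activity": for these, "the last observation carried forward (LOCF) approach will be applied to impute the endpoint when ED measure is available". Neither sentence names an estimand or an endpoint.
- **SAP Table GPHK.6.4, SF-36v2 row.** The rule is split by estimand. The first part reads "For efficacy estimand, missing data will be imputed based on LOCF method", and the second part reads "For hybrid estimand, missing data will be imputed based on Section 6.13.1.3". The hybrid entry makes no exception for an available ED score.
- **SAP 6.13.** For the FDA submission, assessment of the primary and key secondary objectives "will be conducted with multiple imputation of missing data (see Section 6.13.1.3"). The only objective excepted is onset of diabetes.

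Section 6.13.1.3 is itself written for the hybrid estimand. For data missing solely because of exceptional circumstances, "the analysis will consider the missing data as missing at random". For all other missing data, "missing data will be imputed based on retrieved dropouts in the same treatment arm", with placebo-based multiple imputation as the fallback if retrieved dropouts are too few.

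**The concern.** H_1015,12 is one of the hypotheses under familywise error control, and the hybrid analysis is the one meant for the FDA. Its missing-data rule should be unique before treatment codes are opened. As written, a participant with an ED score and no Week 72 score is sent to LOCF by one section and to multiple imputation by two others.

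The two methods are not interchangeable. LOCF assumes that the score at the ED visit would have persisted to Week 72, and it enters that score as if it had been observed. Section 6.13.1.3 draws mainly on participants in the same arm who were assessed after stopping drug, and multiple imputation carries the uncertainty of the filled-in values into the standard error. Both the estimate and its precision can therefore depend on which sentence the programmer follows.

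**Working it through.** **Step 1: which endpoint does the exception reach?** The controlled 72-week endpoints were compared with the Schedule of Activities (Protocol 1.3.1).

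- Body weight, waist circumference and SBP: measured at many post-baseline visits.
- Fasting insulin: Weeks 12, 24, 36, 48, 60 and 72.
- Lipid panel: Weeks 24 and 72.
- SF-36v2: baseline (Visit 3), one nominal Week 72 assessment, and ED.

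Only SF-36v2 has a single scheduled post-baseline measure. In the extracted schedule its two post-baseline marks fall under Visit 99 and ED. The table may be misaligned, but either way there is one Week 72 assessment plus ED.

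**Step 2: the rules side by side, for a participant with an ED score and no Week 72 score.**

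| Source | Efficacy estimand | Hybrid estimand |
|---|---|---|
| SAP 6.4 exception | LOCF | LOCF (no estimand limit) |
| Table GPHK.6.4, SF-36v2 row | LOCF | 6.13.1.3 |
| SAP 6.13 | not addressed | 6.13.1.3 |

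The efficacy column agrees. The hybrid column does not, and the SAP states no order of precedence.

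**Step 3: who is affected.** Only hybrid-estimand participants with an ED score and no Week 72 score. Protocol 7.1 tells those who stop drug to keep attending scheduled visits, so some will have an observed Week 72 score. On the other hand, the Visit 99 procedure lists (Protocol 4.1.1.2.2, SAP 5.1) contain no patient-reported outcomes. If those lists govern, a participant who returns only for Visit 99 is exactly the conflicted case.

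**Step 4: size, as an illustration.** The documents give no effect size, SD or power for SF-36v2, so there is no planned figure to reproduce. Let m be the share affected, assumed equal in both arms. Let gT and gP be the gaps, on tirzepatide and on placebo, between the carried-forward mean change and the mean change imputed by 6.13.1.3. Then

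shift in treatment difference = m × (gT − gP).

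Protocol 9.2 plans 1200 participants on 10 mg and 15 mg together, 600 on placebo, and 25% dropout. If every dropout had an ED score and no Week 72 score, 0.25 × 1200 = 300 and 0.25 × 600 = 150 would be affected. So m = 25% is an upper bound under the planning assumption. The gaps are assumed.

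| m | gT = 1, gP = 0 | gT = 2, gP = 0 | gT = 3, gP = 0 | gT = 2, gP = 1 |
|---|---|---|---|---|
| 5% | 0.05 | 0.10 | 0.15 | 0.05 |
| 10% | 0.10 | 0.20 | 0.30 | 0.10 |
| 25% | 0.25 | 0.50 | 0.75 | 0.25 |

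With equal gaps the shift is zero. If gT is smaller than gP, it is negative.

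**Step 5: precision, as an illustration.** Assume an SD of change of 5 to 10 points.

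- All 1800 values treated as observed: SE = SD × √(1/1200 + 1/600) = SD × 0.050, or 0.25 to 0.50.
- Only 75% observed: SE = SD × √(1/900 + 1/450) = SD × 0.0577, or 0.29 to 0.58.

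The second line is a reference for the information actually observed. It is not a prediction of the multiple-imputation standard error.

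**The case against.** The strongest reply is that the SAP already answers the question. Section 6.4 is a general section that names neither SF-36 nor an estimand, whereas the Table GPHK.6.4 row names the endpoint, the model and a rule for each estimand. Section 6.13 supports the table by applying multiple imputation to every primary and key secondary objective except onset of diabetes. Elsewhere LOCF goes with the efficacy analysis set: Section 6.13.3.1 assigns LOCF or MMRM to the other secondary analyses on that set, and Section 6.15 places patient-reported outcomes there unless specified otherwise. On this reading the 6.4 sentence is a loosely drafted counterpart of the efficacy rule.

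Most of this stands. The table is the more specific text and probably states the intent. A reader might infer that the FDA analysis is wholly open to choice, with neither passage having the better claim; the documents do not support that.

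The reply does not remove the conflict. The 6.4 exception departs from 6.13.1.3, which is written for the hybrid estimand, so its literal reach includes the hybrid analysis. A programmer could follow the table to 6.13.1.3 and still apply the carve-out from it in 6.4.

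It might also be said that LOCF contradicts an estimand defined regardless of adherence. That goes too far. The estimand sets the target, and LOCF is an assumption about unseen values. It is a doubtful assumption for a Week 72 outcome after stopping drug, but that is a criticism of method and not an internal contradiction.

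**Conclusion.** The inconsistency is real but narrow. It concerns one controlled key secondary endpoint, one estimand, and only participants with an ED score and no Week 72 score. The primary endpoints and the efficacy-estimand SF-36 analysis are untouched. It should still be corrected, because 6.4 taken literally would enter ED-time scores as observed Week 72 outcomes in a controlled analysis.

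The size and sign of the effect cannot be determined from the documents. The illustrative shift of 0.05 to 0.15 T-score points at m = 5%, rising to 0.25 to 0.75 at the 25% upper bound, rests on an assumed 1 to 3 point gap on tirzepatide, none on placebo, and the same m in both arms.

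A reader might infer that a quarter of each arm is affected, and that if half the ED-time benefit were later lost, LOCF would overstate the effect by 0.25 × 0.5 = 12.5% of that benefit. The documents do not support this. The 25% is a planning dropout rate and not a count of the conflicted cases, the loss of half has no source, and LOCF would apply on placebo too. Nor is overstatement assured: someone who stops during dose escalation or for gastrointestinal symptoms may have little gain in physical functioning at the ED visit, and carrying that score forward could understate the effect.

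**What to change.** In SAP 6.4, limit the LOCF sentence to the efficacy estimand. Add that, for the hybrid estimand, SF-36v2 Physical Functioning follows Section 6.13.1.3 even when an ED score exists, as Table GPHK.6.4 and Section 6.13 already prescribe. The cost is about one sentence in the SAP, with no change to data collection, sample size or the testing sequence. It should be in place before the Week 72 data are unblinded for analysis.

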6.5. Multicenter Studies

The randomization will be stratified by country, and the country/pooled country will be used as a covariate.

6.6. Multiple Comparisons/Multiplicity

The type 1 error rate control strategy for primary and key secondary efficacy objectives is illustrated in Section 6.13.3. These objectives will be assessed separately for the “efficacy” estimand and “hybrid” estimand. As they are intended for different purposes, no multiplicity adjustments will be made for conducting separate analyses relative to the “efficacy” and “hybrid” estimands. In addition, no multiplicity adjustments will be made for evaluating other secondary and exploratory objectives, and safety assessments.

6.7. Patient Disposition

A listing of study disposition for all randomized participants will be provided at the primary database lock and final database lock, respectively. Summaries of study disposition and study drug disposition for all randomized participants will be provided by planned study treatment at the primary database lock (after 72-week treatment). In addition, similar summaries might be provided for participants without prediabetes at randomization at the primary database lock. Same summaries will be provided for randomized participants with prediabetes at randomization at final lock (after 176-week treatment).

The study completion status is defined as follows:

- at the end of 72-week treatment period (when the primary endpoint is ascertained, and primary database is locked):
 - for participants without prediabetes at randomization: participants with a non-missing body weight measurement at 72-week (Visit 21 or Visit 99) and non-missing safety follow-up visit (Visit 801) will be considered as completers.
 - for participants with prediabetes at randomization: participants with a non-missing body weight measurement at 72-week (Visit 21 or Visit 99) will be considered as completers.
 - otherwise, they will be considered as non-completers.
- at the end of 176-week treatment period for participants with prediabetes at randomization:
 - participants with a non-missing body weight measurement at 176-week (Visit 116 or Visit 199) and non-missing safety follow-up visit (Visit 802) will be considered as completers; otherwise, will be considered as non-completers.

6.8. Historical Illnesses and Preexisting Conditions

The count and percentages of participants with historical illnesses and preexisting conditions will be summarized by treatment group using the Medical Dictionary for Regulatory Activities (MedDRA) Preferred Terms (PTs) nested within System Organ Class (SOC). The SOC will be in alphabetical order. Conditions (that is, PTs) will be ordered by decreasing frequency within SOC. This will be summarized for all randomized participants.

6.9. Patient Characteristics

A listing of participant demographics for all randomized participants will be provided. All demographic and baseline clinical characteristics will be summarized by study treatment for all randomized participants. Baseline demographic and clinical characteristics of special interest include but are not limited to: age (years), sex (female, male), race, ethnicity, height (cm), weight (kg), BMI (kg/m^2), waist circumference (cm), age group (<65 years, ≥ 65 years), BMI group (<30, ≥ 30 and <35, ≥ 35 and <40, ≥ 40 kg/m^2), country, weight-related comorbidities. In addition, similar demographics and baseline characteristics might be provided by study treatment by glycemic status (prediabetes and normoglycemia) at randomization.

All participants without laboratory tests suggestive of diabetes will be classified as having either normoglycemia or prediabetes. Populations are defined in [Table GPHK.6.3](#).

Table GPHK.6.3. Classification of Glycemic Status

	Normoglycemia	Prediabetes	Diabetes
Fasting glucose Obtained alone or at time = 0 during an OGTT	<100 mg/dL (<5.6 mmol/L)	100-125 mg/dL (5.6-6.9 mmol/L)	≥ 126 mg/dL (≥ 7.0 mmol/L)
2H glucose Obtained at time = 120 min during an OGTT	<140 mg/dL (<7.8 mmol/L)	140-mg-199 mg/dL (7.8-11.0 mmol/L)	≥ 200 mg/dL (≥ 11.1 mmol/L)
HbA1c	<5.7% (<39 mmol/mol)	5.7%-6.4% (39-47 mmol/mol)	$\geq 6.5\%$ (≥ 48 mmol/mol)

Abbreviations: HbA1c = hemoglobin A1c; min = minute; OGTT = 2-hour oral glucose tolerance test.

In keeping with American Diabetes Association guidelines (ADA 2019a), at least 2 abnormal tests are required to diagnose prediabetes. Specifically, participants meeting 1 of the following criteria will be categorized as prediabetes:

- Both fasting glucose (FG; 0 hour of OGTT) **and** 2-hour values during the 2-hour OGTT values are in the prediabetes range, which is 100 to 125 mg/dL (5.6 to 6.9 mmol/L) and 140 mg to 199 mg/dL (7.8 to 11.0 mmol/L) for FG and 2-hour OGTT, respectively.

- FG at Screening Visit 1 **and** Visit 2 (0 hour of OGTT) are in the prediabetes range.
- FG at Screening Visit 1 **and** 2-hour values during 2-hour OGTT are in the prediabetes range.
- HbA1c AND 1 of either the FG (Visit 1 **or** Visit 2) or 2-hour OGTT values are in the prediabetes range. For HbA1c, the prediabetes range is 5.7% to 6.4% (39 to 47 mmol/mol).
- Any 2 of HbA1c values between Visit 1 and Visit 3 including unscheduled visits are in the prediabetes range.

6.10. Concomitant Therapy

Concomitant medication will be summarized by PTs by treatment group by decreasing frequency for SS group. The following 2 postbaseline periods will be considered, respectively:

- up to 72 weeks plus safety follow-up (Visit 801) for all randomized participants, and
- up to 176 weeks plus safety follow-up (Visit 801 or Visit 802) for participants with prediabetes at randomization.

Additionally, medications of interest (as defined below) will be summarized by treatment for SS.

Concomitant medications of interest include the following:

- baseline antihypertensive therapy
- baseline lipid lowering therapy
- changes to baseline medication in post-randomization (in term of type/class and dose):
 - antihypertensive therapy, and
 - lipid lowering therapy.
- utilization after randomization of:
 - antihyperglycemic medication for the treatment of diabetes for participants who develop T2DM during the study (antihyperglycemic medication for the treatment of prediabetes is not allowed pre protocol)
 - antidiarrheal medication. and
 - antiemetic medication.

6.11. Treatment Exposure and Compliance

6.11.1. Study and Study Treatment Exposure

Summary of duration of follow-up (defined as time in days from date of randomization to the date of the last study visit) and/or duration on study treatment (defined as time in days from date of first dose of study treatment to date of last dose of study treatment plus 7 days) will be provided by treatment group using data from SS, in the following 2 periods:

- 72 weeks plus safety follow-up (Visit 801) for all randomized participants. and
- 176 weeks plus the safety follow-up periods (Visit 801 or Visit 802) for participants with prediabetes at randomization.

For the summary of duration on study treatment, the frequency and percentage of participants falling into the following range will be summarized by planned treatment group as well:

- >0
- ≥ 4 weeks
- ≥ 8 weeks
- ≥ 12 weeks
- ≥ 16 weeks
- ≥ 20 weeks
- ≥ 24 weeks
- ≥ 36 weeks
- ≥ 48 weeks
- ≥ 52 weeks
- ≥ 72 weeks
- ≥ 98 weeks
- ≥ 124 weeks
- ≥ 150 weeks, and
- ≥ 176 weeks.

In addition, the frequency and percentages of participants falling into the following study treatment exposure ranges may be summarized by planned treatment group:

- 0 weeks
- >0 to <4 weeks
- ≥ 4 to <8 weeks
- ≥ 8 to <16 weeks
- ≥ 16 to <24 weeks
- ≥ 24 to <36 weeks
- ≥ 36 to <48 weeks
- ≥ 48 to <52 weeks
- ≥ 52 to <72 weeks
- ≥ 72 to <98 weeks (for participants with prediabetes at randomization)
- ≥ 98 to <124 weeks (for participants with prediabetes at randomization)
- ≥ 124 to <150 weeks (for participants with prediabetes at randomization)
- ≥ 150 to <176 weeks (for participants with prediabetes at randomization), and
- ≥ 176 (for participants with prediabetes at randomization).

No p-values will be reported in these summaries as they are intended to describe the study populations rather than test hypotheses about them.

6.11.2. Compliance to Study Treatment

Summary of prematurely discontinuing study treatment (including discontinuation reason) will be provided by study treatment. A time-to-event analysis of premature study treatment discontinuation will also be conducted.

The analyses related to compliance will be conducted for the following 2 periods separately:

- during the 72-week treatment period for all randomized participants, and
- during the 176-week treatment period for participants with prediabetes at randomization.

If data warrants, the counts and percentages of participants who follow the planned escalation scheme, have dose interruption, or have dose de-escalation may be summarized for tirzepatide treatment group. In addition, the proportion of participants receiving 2.5 mg, 5 mg, 7.5 mg, 10 mg, 12.5 mg, or 15 mg may be presented by randomized tirzepatide treatment and visit during the dose escalation period.

Treatment compliance will be defined as taking at least 75% of the scheduled tirzepatide doses. Compliance over the study period will be calculated using the number of doses administered (regardless of the actual dose in mg administered) divided by the total number of doses expected to be administered $\times 100$ over the study period. Treatment compliance will be summarized descriptively in the study period by treatment using the mITT population.

6.12. Important Protocol Deviations

Important protocol deviations are identified in the Trial Issues Management Plan (TIMP). A listing and a summary of important protocol deviations by treatment will be provided at the end of 72 weeks treatment (for all randomized participants) and at the end of the study (for participants with prediabetes at randomization).

